### **Statistical analysis**

The results will be presented using descriptive statistics mean  $\pm$  standard deviation (SD) for variables with normal distribution and median (minimum – maximum) for non-parametric data. The normality of data distribution will be assessed using the Kolmogorov-smirnov test. In order to compare the neuromuscular characteristics, food intake and body composition of both groups, the T Test - independent, or the non-parametric alternative, Mann Withney's U

Test will be used. To assess whether the protein intake of strict vegetarians and non-vegetarians reaches the daily recommendation, the simple T-test or Wilcoxon's Test for Single Sample will be used, according to the data distribution. For correlations between neuromuscular parameters, food intake and body composition of strict vegetarians and non-vegetarians, the Pearson test ( $r$ ) will be used for continuous variables that presented normal distribution and the Spearman (Rho) test will be used when the variable does not present a normal distribution and/or or in ordinal variable. Correlation values (  $r$  or Rho ) will be classified as: "biologically negligible" (between 0.3 and -0.3); "weak" (between 0.31 and 0.5 or -0.31 and -0.5); "moderate" (between 0.51 and 0.7 or -0.51 and -0.7); "strong" (between 0.71 and 0.9 or -0.71 and -0.9); and "very strong" (when  $> 0.9$  or  $< -0.9$ ) (MUKAKA, 2012). The level of physical activity will be evaluated using the chi-square test of homogeneity of proportions. Calculations will be performed in SPSS software (version 25) and a significance level of 5% ( $p > 0.05$ ) will be adopted.

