## Sample size calculation

The sample size was calculated generating 2 experimental groups: strict vegetarians (SV) and non-vegetarians (NV). 5% significance level and 95% statistical power will be considered. The result of the calculation (72 participants) was considered with a possible sample loss of 22.2%. Thus, 44 subjects will be needed in each group, totaling 88 participants. The sample size was calculated using the SAS Studio software (SAS Institute Inc., Cary, NC, USA).

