## **Logistics**

The recruitment of individuals for research will take place in a continuous flow, through dissemination through posters that will be fixed on the university premises, flyers that will be distributed at the Ecological Fair of Redenção (where there is a large circulation of vegetarians), vegetarian restaurants in region, as well as through social networks. Interested parties may contact the team via email, social media or in person. After the preliminary verification of the inclusion and exclusion criteria, a virtual meeting (phone or video call) will be held to provide information about Phases I (baseline) and II (16 weeks of strength training protocol participation) of the study and also to clarify doubts. Interested parties will be informed that participation in Phase I of the study is not conditioned to participation in Phase II, since, even if there is interest, only those who meet the specific eligibility criteria for such, referring to the evaluation of the average daily protein intake. Interested parties will receive a virtual copy of the Free and Informed Consent Term, which will clarify the research objectives and other relevant aspects, and will only participate in the research upon confirmation of agreement with the Term, which can be obtained by text, image or audio. Then, participants will be instructed to complete the 3-day food record and also to count the number of steps with the pedometer during 7 consecutive days. In the week following the end of data collection, participants will be invited to attend face-to-face assessments at the Exercise Research Laboratory at UFRGS.

At the first meeting, an anamnesis will be applied, body mass and height will be evaluated to determine the body mass index for a detailed review of the eligibility criteria. Then, the following evaluations will be performed: Body composition (Anthropometry, Dual Emission X-ray absorptiometry and ultrasonography), maximum and dynamic strength by isokinetic dynamometer (familiarization) and vertical jump power (familiarization). On the same day, the

International Physical Activity Questionnaire will be applied to also assess the participants' level of physical activity (CRAIG et al., 2003).

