A second face-to-face meeting will be scheduled with an interval of at least 48 hours after the first one to carry out the maximum and dynamic strength by isokinetic dynamometer and vertical jump power tests. Also, the knee extensors, knee flexors and plantar flexors, one maximum repetition test (1MR) familiarization will be realized. At third face-to-face meeting, the 1MR tests of knee extensors, knee flexors and plantar flexors will be evaluated. Body composition assessments of all participants and performance tests will be performed by physical educators. The 3-day food record and anamnesis will be performed and analysed by a nutricionista, equally trained for these tasks. Thus, the participants will started the 16 weeks of strength training protocol. After 1 week of the ending of strength training protocol the participants will repeat the measurements and tests realized at baseline in more three days to of face-to-face meeting. All face-to-face meetings with the participants to carry out the assessments will take place in the Neuromuscular Sector of the Exercise Research Laboratory, located at the School of Physical Education, Physiotherapy and Dance at UFRGS.

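### Must the plan be changed because its 72 participants are tied to no outcome and three domains are compared at an unadjusted 5%?

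*Combined protocol and SAP*

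**What the plan says.** The Sample size calculation section sets up two diet groups, strict vegetarians and non-vegetarians, and says "5% significance level and 95% statistical power will be considered". It then says "The result of the calculation (72 participants) was considered with a possible sample loss of 22.2" percent, which leads to 44 per group and 88 in all. The only other detail is the software. Outcome, effect, SD, test, sidedness and phase are not given there.

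The Statistical analysis section says "In order to compare the neuromuscular characteristics, food intake and body composition of both groups, the T Test - independent", with Mann-Whitney as the non-parametric alternative. One-sample tests of protein intake, correlations and a chi-square test of activity level follow, all under one 5% level. No comparison is called primary or confirmatory, and no adjustment is mentioned.

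Logistics describes "Phases I (baseline) and II (16 weeks of strength training protocol participation) of the study" and adds that "participation in Phase I of the study is not conditioned to participation in Phase II". The baseline measurements are repeated after training. They include "Body composition (Anthropometry, Dual Emission X-ray absorptiometry and ultrasonography), maximum and dynamic strength by isokinetic dynamometer" and vertical jump power. At a later visit "the 1MR tests of knee extensors, knee flexors and plantar flexors will be evaluated". On diet, "The 3-day food record and anamnesis will be performed and analysed by a nutricionista".

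**The concern.** Power belongs to one comparison at one effect size. A claim of 95% power with neither attached cannot be checked, and a reader cannot tell whether the 72 are baseline entrants or people who complete training.

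The analysis section adds to the doubt. It covers three domains, each measured in several ways and on two occasions. It does not say whether baseline, post-training or change values are compared between diets, and it lists no before-after test although the study has a 16-week training phase. If nothing elsewhere fixed the main comparison, the investigators could choose it after seeing the results. A chance finding could then be reported as an effect of diet, with 95% power quoted beside it.

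**Working it through.** **1. The plan's own figure.** The 72 cannot be reproduced, because no effect, SD or test is given. The step to 88 can: 72 × 1.222 = 87.98, or 44 per group.

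**2. What 72 implies.** Assume 36 per group, an independent t test and 5% significance. The normal approximation to the detectable difference is (1.960 + 1.645) × √(2/36) = 0.85 SD. The noncentral t distribution gives the exact values below. The 0.5 SD effect is an assumption for illustration.

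| Analysed per group | Sides | Difference for 95% power | Power at 0.5 SD |
|---|---|---|---|
| 36 | two | 0.86 SD | 55% |
| 36 | one | 0.78 SD | 68% |
| 34 | two | 0.89 SD | 53% |
| 44 | two | 0.78 SD | 64% |

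The row for 34 applies the stated loss to the enrolled number: 88 × (1 − 0.222) = 68.5, about 34 per group. Reaching 95% power at 0.5 SD would take 105 per group.

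The table shows what 72 could detect. It does not show that 72 is wrong, because the documents give no target effect to compare with 0.86 SD.

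**3. Multiplicity.** Counting one variable per method in Logistics gives three one-repetition-maximum tests, two isokinetic measures, jump power, DXA, ultrasonography and anthropometry: nine. Food intake would make ten.

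Suppose all nine are truly equal between groups and any one p-value below 0.05 counts as success. If independent, the chance of at least one false positive is 1 − 0.95⁹ = 0.370. Simulation of 40,000 trials with 36 per group and equal correlation between all outcomes gave:

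| Assumed correlation | Chance of at least one false positive |
|---|---|
| 0 | 0.369 |
| 0.5 | 0.274 |
| 0.9 | 0.127 |

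Adding food intake gives 1 − 0.95¹⁰ = 0.401 if independent. That case should be set aside. The groups are defined by diet, so a difference in food intake is expected and cannot be treated as a null outcome.

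The count, the correlations and the success rule are all assumptions. The documents give none of them.

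**4. Time point.** The independent t test can be applied to baseline values, post-training values or changes. With two groups and two occasions, a t test on change scores is equivalent to the group-by-time interaction test. The stated method can therefore answer whether training response differs by diet. The text leaves out which values enter the test, and any test of training response within a group.

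**The case for a change.** The strongest case for a change is that the two sections concerned appear complete and neither refers to a primary outcome. Even if one is defined elsewhere, the sample size and the analysis are not linked to it. Writing the link down would cost a few sentences and no data. Even at a correlation of 0.9, the false-positive chance under the any-success rule is more than twice 5%. A training study whose statistical section never mentions change over time is also an uncomfortable omission.

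Much of this stands as a description. The inputs to the 72 are undocumented, the time point is unstated, and a test of training response is not listed.

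It does not stand as proof of an error. The text immediately before the statistical section, a natural place for outcome definitions, was not available, so the absence of a primary outcome cannot be held against the plan. The plan does not say that one significant result among many establishes a diet effect. The request also amounts to asking the investigators to record whatever outcome, effect, test and phase they used. It supplies no corrected sample size and no replacement analysis, because the documents provide no basis for either.

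**Conclusion.** No change to the plan follows. The concern identifies missing detail, not a wrong number or a wrong rule. The 72 agrees with a two-sided t test at about 0.86 SD (0.78 SD one-sided), assuming 36 per group are analysed. Whether that effect is realistic cannot be judged from the documents. The range of about 13% to 37% illustrates multiplicity for nine null measures at one time point, under a success rule the plan does not contain. It does not measure this plan's error rate.

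The investigators can fill the gap sensibly. They hold the sample-size calculation, and the stated between-group test works on change scores as well as on single-occasion values. A reader of the eventual report should expect it to state the inputs behind the 72, the phase and occasion of each comparison, and which comparison was the main one. This conclusion depends on the unavailable text. If it names no primary outcome, the reporting gap is wider, but the stated figures would still not be shown to be wrong.

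### Correlations between -0.3 and 0.3 are labelled biologically negligible from the point estimate alone, although at the planned sample sizes most such values are compatible with a correlation the plan itself calls weak or moderate

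*Combined protocol and SAP*

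**What the plan says.** The Statistical analysis section plans Pearson or Spearman coefficients: "For correlations between neuromuscular parameters, food intake and body composition of strict vegetarians and non-vegetarians". It does not say whether the two dietary groups are analysed separately or together. Each coefficient is then classified by its value. The lowest band is "biologically negligible' (between 0.3 and -0.3") and the next is "weak' (between 0.31 and 0.5 or -0.31 and -0.5"), followed by moderate (0.51 to 0.7), strong and very strong. A source is cited for the scale. The label depends on neither a confidence interval nor a p-value, and no interval is planned for any correlation. The section separately adopts "a significance level of 5" per cent.

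The Sample size calculation section describes a two-group calculation ("The sample size was calculated generating 2 experimental groups: strict vegetarians (SV) and non-vegetarians (NV")) with these settings: "5% significance level and 95% statistical power will be considered". It gives 72 participants before loss and then states that "44 subjects will be needed in each group, totaling 88 participants". It names no target correlation.

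**The concern.** Four of the five labels describe only size. The lowest one adds a judgement about biological importance and takes it from the point estimate, however imprecise that estimate is. A coefficient of 0.2 or 0.28 from a few dozen women may come from a true correlation that the same scale would call weak or even moderate. If it is reported as biologically negligible without an interval, the reader cannot tell a precisely small correlation from an undetermined one. What is at stake is how the trial describes the relation of food intake to strength and body composition.

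**Working it through.** **Inputs.** From the Sample size calculation section: 72 participants before loss (36 per group if split equally), 22.2% loss, and 44 per group or 88 in total. From the Statistical analysis section: a band edge of 0.3 and a 5% level. Assumptions: two-sided tests, equal groups, bivariate normality for Pearson's r. Because pooling is not specified, I use n = 36 and 44 (per group) and n = 72 and 88 (pooled).

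**The plan's own figure.** 72 × 1.222 = 87.98, so 88; 36 × 1.222 = 43.99, so 44. The stated total is reproduced by adding 22.2% to 72. The 72 itself cannot be reproduced, because no effect size or SD is given.

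**Formulas.**
- 95% CI (Fisher z): tanh[atanh(r) ± 1.96/√(n − 3)].
- Largest absolute r whose whole CI stays inside ±0.3: tanh[atanh(0.3) − 1.96/√(n − 3)].
- Critical r at two-sided 5%: t/√(n − 2 + t²), with t on n − 2 degrees of freedom.
- Chance that a true correlation ρ falls in the lowest band: Φ{[atanh(0.3) − atanh(ρ)]·√(n − 3)} − Φ{[−atanh(0.3) − atanh(ρ)]·√(n − 3)}.

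**One case in full.** For r = 0.28 and n = 36, atanh(0.28) = 0.288 and 1.96/√33 = 0.341. The limits on the z scale are -0.053 and 0.629, which give a CI of about -0.05 to 0.56.

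**Results.**

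| n | 95% CI at r = 0 | 95% CI at r = 0.2 | Largest absolute r with CI inside ±0.3 | Critical r | Labelled negligible if true r = 0.40: formula (simulation) |
|---|---|---|---|---|---|
| 36 | -0.329 to 0.329 | -0.14 to 0.50 | none | 0.329 | 26% (24%) |
| 44 | -0.297 to 0.297 | -0.10 to 0.47 | 0.003 | 0.297 | 23% (22%) |
| 72 | -0.232 to 0.232 | -0.03 to 0.41 | 0.073 | 0.232 | 17% (16%) |
| 88 | -0.209 to 0.209 | -0.01 to 0.39 | 0.097 | 0.210 | 15% (14%) |

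The simulation used 100,000 bivariate-normal samples per setting. A further simulation with r rounded to two decimals, as the bands imply, gave about 25%, 23% and 15% at n = 36, 44 and 88. For a true r of 0.35 it gave 38%, 36% and 31%. For a true r of 0.50 the formula gives 8%, 6%, 2% and 1% at the four sizes.

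**How much of the band is affected.** At n = 36 the bound is negative (-0.032), so even r = 0 has a CI that leaves the band. At n = 44 only values within 0.003 of zero qualify. Pooled, the share of the band in which the CI crosses ±0.3 is (0.30 − 0.073)/0.30 = 76% at n = 72 and (0.30 − 0.097)/0.30 = 68% at n = 88. Keeping the CI inside the band would need n = 44 at an observed r of 0, 91 at 0.1 and 340 at 0.2.

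**Overlap with significance.** If the groups are pooled, absolute values from 0.232 (n = 72) or 0.210 (n = 88) up to 0.30 are both significant at 5% and labelled negligible. At r = 0.25, p = 0.034 and 0.019 respectively. At n = 44 the overlap is only 0.297 to 0.30, and at n = 36 there is none.

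**Spearman.** Multiplying the standard error by √1.06 widens the interval slightly: at n = 36 and Rho = 0 it runs from -0.338 to 0.338.

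**The case against.** The strongest reply is that the plan only sorts coefficients into size bands from a cited scale. A reader might infer that the plan declares absence of association for anything in the lowest band. The text states no such conclusion, and that reading should not be pressed.

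A reader might also infer that this sample could never support the word negligible. That is exact only at n = 36. At n = 44 there is a trivial exception near zero, and pooled it is attainable for absolute r up to about 0.07 to 0.10.

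A third tempting reading is that a significant correlation labelled negligible is a contradiction. It is not: the p-value asks whether the correlation is zero, while the band describes its size. The overlap also arises mainly under pooling, which the plan leaves open.

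The labelling probabilities are partly what any cut-point does, and they run both ways. At n = 36 a true r of 0.40 is labelled moderate or stronger in about 23% of samples, and a true r of 0.25 is labelled weak or stronger in about 37%. Finally, allowing the word negligible only when the whole CI lies inside ±0.3 would nearly abolish the category per group.

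All of this stands, and it limits the point to interpretation. It does not remove the remaining defect, which is that a judgement of biological unimportance is attached to an imprecise estimate reported without an interval. A source for the size scale does not supply precision.

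**Conclusion.** The concern holds in a limited form. Per group, practically no coefficient in the lowest band can exclude a true correlation beyond ±0.3; pooled, about the outer 68% to 76% of the band cannot. The chance of the label for a true correlation of 0.40, near the middle of the plan's weak band, falls from about one in four at 36 per group to about one in seven at 88 pooled. The documents do not support the stronger claims that the plan asserts no association or contradicts its own significance level.

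The correlations have no stated sample-size basis, so neither the 88 nor the power is affected. These figures rest on two-sided 5% tests, equal groups, bivariate normality and final numbers between 36 and 44 per group. The change is worth making before analysis because it governs what can be concluded from the correlations.

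**What to change.** In the Statistical analysis section:
- Report every r or Rho with its 95% CI.
- Drop the word biologically from the lowest band.
- Say that all five bands describe only the size of the point estimate.
- Add that a coefficient will not be interpreted as showing no important association when its CI extends beyond ±0.3; such a result is inconclusive on that question.
- State whether correlations are run within each dietary group, pooled, or both.

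The cost is a few sentences and an interval that needs only the coefficient and n (with the wider standard error for Rho). No new data or participants are required. The downside is that more small correlations, and nearly all of them if the analysis is per group, will be reported as inconclusive.
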